9.4.4. Safety Analyses

Analysis of Adverse Events

Safety analyses will be performed on the Safety Population. AEs will be coded using MedDRA. Incidences (number and percent) of TEAEs, those events that start after dosing or worsened in severity after dosing, will be presented by treatment group. Incidences of TEAEs will also be presented by maximum severity and relationship to study medication.

Similar presentations will be provided for serious AEs, AEs leading to withdrawal from the study, or AEs leading to death. Analysis of AE data will include examination of the incidence rates of TEAEs and index hip TEAEs following the first dose and second dose, as well as the cumulative incidence of TEAEs after all doses of FX006.

Other Safety Analyses

Laboratory data, vital sign information and X-ray data will be presented as descriptive summary statistics for value and change from Baseline at each individual time point. Categorical variables will be summarized by frequencies and percentages.

CONFIDENTIAL Page 65 of 72

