6.3. Open Label Phase Objectives

6.3.1. Secondary Objective:

To examine efficacy following a second injection of FX006 in patients with hip OA

6.3.2. Primary Objective:

• To assess the overall safety of a second injection of FX006 in patients with hip OA

CONFIDENTIAL Page 29 of 72

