7. INVESTIGATIONAL PLAN

7.1. Overall Study Design and Plan

This is a two-part, multi-center, randomized, double-blind, placebo-controlled, parallel-group study in patients with hip OA. Approximately 70 patients will be enrolled in Part I and approximately 440 patients will be enrolled in Part II of the study. In each part, patients will be randomized to one of two treatment groups (1:1) and treated with a single IA injection of either 32 mg FX006 or normal saline.

Eligible patients will be randomized within strata defined by Baseline Western Ontario and McMaster Universities Osteoarthritis Index (WOMAC) A (pain) (0-10 numeric ratings scale (NRS) average of Screening 2 and Day 1 with the following classifications: 5.0 to < 6.0, 6.0 to < 7.0, and $\geq 7.0 \text{ to} 9.0$ (see Section 9 for details).

FX006 or saline placebo will be administered as a single IA injection with a 12-week follow-up period in the double-blind phase.

Patients participating in Part I of the study will be treated with a single IA injection of either 32 mg FX006 or normal saline and will return for follow up visits at Weeks 12, 16, 20, and 24 or up until the time of this amendment. The patients will be discontinued at the time of notification by the Investigator.

Patients participating in Part II of the study will be treated with a single IA injection of either 32 mg FX006 or normal saline and will return for follow up visits at Weeks 12, 16, 20, and 24. Patients who are eligible for the second injection in the open-label phase at Week 12 will receive an open-label injection of FX006 at Week 12 and return for follow-up visits at Weeks 16, 20, and 24. These patients will complete the study at Week 24.

Patients participating in Part II of the study that are not clinically indicated for a second injection at Week 12 will return to the clinic at Weeks 16, 20, and 24 and will receive an open-label injection of FX006 at the first evaluation where the patient has been determined to meet all criteria. Patients will then return for follow-up visits every 4 weeks for 12 weeks post second injection and will complete the study 12 weeks post second injection (e.g., Week 24, 28, 32, or 36 depending on when the patient receives the open-label injection).

Patients participating in Part II of the study who are not eligible for a second injection after evaluation at Weeks 12, 16, 20, and 24 will complete the study at the Week 24 visit and complete the End of Study (EOS) assessments.

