7.4.4. Second Injection Inclusion Criteria (Part II Patients Only)

To be eligible to receive the second injection during the open-label phase, patients must fulfill the following criteria:

- 1. Completed the double-blind phase of the study through Week 12
- 2. No major safety concerns during the initial dose period (including allergic reaction to initial dose of study medication) as assessed by the Investigator and patient
- 3. Clinically indicated to receive FX006, in the opinion of the Investigator and patient
- 4. WOMAC A (pain) score of ≥ 3 (0-10 NRS)
- 5. Compliant with study procedures and visit schedules up to the open-label injection with FX006 and the willingness and ability to continue to comply for additional 12 weeks after the second injection
- 6. Willingness to continue abstaining from use of protocol-restricted medications during the study (Refer to Section 7.6.2)

CONFIDENTIAL Page 37 of 72

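### Part II reports crude TEAE percentages after the first and second dose with no common time window, so the second dose will tend to look safer simply because it is watched for less time

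*Protocol*

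**What the plan says.** Protocol 9.4.4 sets the measure: "Incidences (number and percent) of TEAEs, those events that start after dosing or worsened in severity after dosing, will be presented by treatment group". It then adds "examination of the incidence rates of TEAEs and index hip TEAEs following the first dose and second dose", and also "the cumulative incidence of TEAEs after all doses of FX006". None of the three has a time window or a person-time denominator. The synopsis confines the by-dose and cumulative summaries to Part II.

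Protocol 7.1 sets the time at risk. A Part II patient not re-injected at Week 12 is reassessed at each four-weekly visit up to Week 24. Such a patient "will receive an open-label injection of FX006 at the first evaluation where the patient has been determined to meet all criteria". A re-injected patient "will complete the study 12 weeks post second injection". A patient who never qualifies "will complete the study at the Week 24 visit and complete the End of Study (EOS) assessments".

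Protocol 7.4.4 sets the switch conditions. They include WOMAC A of at least 3, clinical indication in the view of investigator and patient, compliance, and no major safety concern after the first dose.

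Protocol 6.3 gives the primary objective of the open-label phase: "To assess the overall safety of a second injection of FX006 in patients with hip OA". The by-dose TEAE summary is the stated analysis that addresses it.

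**The concern.** A percentage of patients with at least one event grows with the time watched. The first-dose column would accumulate events over 12 to 24 weeks and the second-dose column over 12. Side by side, the second dose gains an advantage that owes nothing to the drug, on the question that the open-label phase exists to answer.

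The end of the first-dose period also depends on outcome, because pain and clinical indication are among the switch conditions. If FX006 works, its patients may switch later than placebo patients and stay longer in the first-dose period. If that period were left open past Week 12, the extra time would count against FX006 in the randomized comparison.

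The exposure summaries in Protocol 9.4.2, including the time between injections, would show the reader that follow-up differs. They do not enter the AE percentages.

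**Working it through.** **Time at risk.** The documents give no figure for the AE comparison itself. Their visit schedule reproduces: a second injection at Week 12, 16, 20 or 24, plus 12 weeks, gives an end of study at Week 24, 28, 32 or 36, as Protocol 7.1 states. For patients who complete Week 12, first-dose time is therefore 12, 16, 20 or 24 weeks (24 for those who never switch), against 12 after the second dose. Earlier dropouts have less.

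**Inputs for scale (assumptions).** Protocol 5.2.7 gives a TEAE figure of 46.0% for FX006 in the pooled knee studies, at any dose and with no follow-up length stated. It is read here as a 24-week risk. The hazard is constant and equal for both doses and both arms. A share p is re-injected at Week 12, and the rest are followed on the first dose to Week 24.

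**Dose comparison.**
- h = −ln(1 − 0.46)/24 = 0.0257 per week.
- 12-week risk F12 = 1 − exp(−12h) = 1 − √0.54 = 26.5%; F24 = 46.0%.
- First-dose column = p × F12 + (1 − p) × F24. The excess over the second-dose column is (1 − p) × (F24 − F12) = (1 − p) × 19.5 points.
- p = 0.5: 36.3% v 26.5%, an excess of 9.7 points from unrounded values.
- p = 0.7: 32.4% v 26.5%, an excess of 5.8 points.

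Other risk levels and a front-loaded hazard, at p = 0.5:

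| Hazard | 12-week risk | 24-week risk | First-dose column | False excess, points |
|---|---|---|---|---|
| constant | 10.0% | 19.0% | 14.5% | 4.5 |
| constant | 16.3% | 30.0% | 23.2% | 6.8 |
| constant | 26.5% | 46.0% | 36.3% | 9.7 |
| constant | 46.0% | 70.8% | 58.4% | 12.4 |
| 4 times higher in Weeks 0–4 | 26.5% | 37.0% | 31.7% | 5.2 |

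For the last row, hazard-weighted time is 4 × 4 + 8 = 24 units at Week 12 and 4 × 4 + 20 = 36 at Week 24. So F24 = 1 − 0.735^(36/24) = 37.0%.

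**Arm comparison, if the first-dose period is left open.** The false gap is (p placebo − p FX006) × 19.5 points.
- 70% v 60% re-injected at Week 12: 1.9 points.
- 70% v 50%: 32.4% v 36.3%, or 3.9 points.
- With switches spread over Weeks 12, 16, 20 and 24-or-never, shares of 60/10/10/20 (placebo) v 50/10/10/30 (FX006) give 32.5% v 34.4%, or 1.9 points. Shares of 70/10/5/15 v 40/15/10/35 give 30.8% v 35.8%, or 5.0 points.
- The front-loaded hazard cuts these last two gaps to 1.0 and 2.6 points.

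**With matched windows.** Under either hazard shape, a common 12-week window after each dose gives 26.5% for both doses. Cutting at Week 12 makes the arm gap zero.

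**The case against.** The strongest reply concerns the arms. A reader might infer that the FX006 v placebo comparison is bound to be distorted as well. The documents do not support that. The double-blind phase lasts 12 weeks in both arms. The Part I SAP (4.11.1) tabulates AEs by arm for Baseline to Week 12 and then Week 12 to the last visit, and Protocol 9.1 says both parts are analysed alike. If that first table is carried into Part II, the arm problem does not arise. This stands, and the arm point is conditional. It is not fully closed: 9.4.4 states no cut-off, and neither does the unblinded analysis planned for the end of the double-blind phase (9.1.1), by which time early enrollees will be past Week 12.

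The same split does not rescue the dose comparison, because it is not by dose. In Part II its second period would mix late first-dose events with second-dose events.

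Second, 9.4.4 is a summary, the Part II SAP is a separate document not available here, and the protocol speaks of examining rates without specifying a test. All true. But a descriptive table can mislead without a p-value, and the stated measure is number and percent.

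Third, the re-injection shares have no source. At the planned effect (difference 0.65, SD 2.0), a normal approximation that applies that SD to Week 12 pain limits the arm difference in the share with WOMAC A of at least 3 to 2Φ(0.1625) − 1 = 13 points. That makes the false arm gap about 2.5 points (2.0 to 3.3 for SD 2.5 to 1.5), provided the other criteria do not widen it. With 220 per arm and incidence near 34%, the standard error of an arm difference is √(2 × 0.34 × 0.66/220) = 4.5 points. The arm effect is therefore modest against sampling noise.

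**Conclusion.** The dose comparison, as 9.4.4 is written, favours the second dose whenever hazards are equal. The direction follows from the visit schedule as long as some patients stay on the first dose past Week 12 and events continue to occur there. The size does not follow from the documents. About 36% v 26.5% rests on a constant hazard, a 24-week reading of the 46% knee figure and half of patients re-injected at Week 12. The front-loaded case roughly halves the gap, to 5.2 points.

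The arm comparison is only open to distortion. It needs a first-dose period left open past Week 12 and different switch times by arm. The size is then about 2 to 4 points under moderate assumptions, against FX006 if it works.

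A reader might also infer that pain alone decides the switch, or that equal windows would make the dose comparison clean. Neither holds. Clinical judgment, compliance and first-dose safety also decide it, and selection on tolerability favours the second dose whatever the window.

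This should be changed: it bears on the primary objective of the open-label phase, and the Part II SAP can still settle it.

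**What to change.** In Protocol 9.4.4 and the Part II SAP:

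1. Compare first-dose TEAEs with onset from Day 1 to the Week 12 visit, before any second injection, with second-dose TEAEs in the 12 weeks after re-injection.
2. Use Day 1 to Week 12 for the FX006 v placebo comparison.
3. Tabulate later first-dose events separately, per patient-week at risk, censored at the second injection.
4. Present second-dose results by randomized arm, because for placebo-first patients that injection is their first FX006 dose. Make the first v second FX006 dose comparison within FX006-randomized patients who received both. State that these patients were selected on first-dose tolerability and that equal windows do not remove this.

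The cost is wording and one or two more tables. AE onset and injection dates are already collected. The one drawback is that late first-dose events move to a table of their own.

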10. DATA QUALITY ASSURANCE

At the time the study is initiated, the clinical study monitor will thoroughly review the final protocol and the eCRF with the Principal Investigator and staff. During the course of the study, the clinical study monitor will visit the clinical site regularly to check the completeness of the patient records, the accuracy of entries into the eCRF, the adherence to the final protocol and to International Conference on Harmonisation GCP, the progress of enrollment, and the storage, dispensing and accountability of study medication. The Principal Investigator and key study personnel should be available to assist the clinical study monitor during these visits.

The Principal Investigator will give the monitor, auditor(s), Sponsor, Sponsor designee and regulatory authorities direct access to relevant clinical records to confirm their consistency with the eCRF entries. No information in these records about the identity of the patients will leave the clinical site. The Sponsor will maintain the confidentiality of all patient records.

Source data is all information in original records and certified copies of original records of clinical findings, observations, or other activities in a clinical trial necessary for the reconstruction and evaluation of the trial. Source data are contained in source documents (original records or certified copies).

Independent clinical quality assurance audits may be performed at any time during or following completion of the Study by the Sponsor, or its authorized agents, and Competent Authorities and/or the IRB/EC.

CONFIDENTIAL Page 66 of 72

11. DATA HANDLING AND RECORDKEEPING

11.1. Case Report Forms

The eCRF will be supplied by the Sponsor or designee and should be handled in accordance with the instructions provided. All study data should initially be documented in source documents (e.g., patient charts, notes, laboratory reports, ECG recordings, etc.) and then subsequently entered from the source into the eCRF. All eCRFs should be filled out completely by examining personnel or the study coordinator. The eCRF is reviewed, signed, and dated electronically by the Principal Investigator.

11.2. Study Medication Accountability

All study medication required for completion of this study will be provided by the Sponsor or designee. Study medication will be acknowledged upon receipt indicating shipment content and condition. Damaged supplies will be replaced.

Accurate records of all study medications received by, dispensed from, or returned by the study site should be maintained within the Drug Tracking Module.

In the event of a product complaint, complete the Complaint Notification Form located in the Pharmacy binder.

11.3. Rescue Medication Accountability

Each patient will be provided with a sufficient quantity of acetaminophen/paracetamol 500 mg tablets at each scheduled clinic visit starting at Screening.

Patients will bring back the used and unused bottles at the next visit to allow for medication accountability.

11.4. Confidentiality of Data

Patient medical information obtained by this study is confidential, and disclosure to third parties other than those noted below is prohibited.

Upon the patient's permission, medical information may be given to his or her personal physician or other appropriate medical personnel responsible for his or her welfare.

Data generated by this study must be available for inspection by representatives of Competent Authorities, the Sponsor or their representative, and the IRB/EC.

To maintain patient privacy, all eCRFs, study drug accountability records, study reports, and communications will identify the patient by initials where permitted and/or by the assigned patient number. The patient's confidentiality will be maintained and will not be made publicly available to the extent permitted by the applicable laws and regulations.

11.5. Retention of Records

In accordance with US federal regulations (21 CFR 312.62[c]), the Sponsor requires that records and documents pertaining to the conduct of this study and the distribution of study medications, including eCRFs, consent forms, laboratory test results, source data, and medical inventory

CONFIDENTIAL Page 67 of 72

records, must be retained by the Principal Investigator for 2 years after marketing application approval. If no application is filed, these records must be kept 2 years after the investigation is discontinued and the regulatory authorities are notified. The Sponsor or their representative will notify the Principal Investigator of these events. In the event that local regulations are more stringent than that specified above, the local regulations will be adhered to. If local records retention regulations are more stringent than that specified above, the local regulations will prevail.

11.6. Protocol Adherence

The Principal Investigator must adhere to the protocol as detailed in this document and agrees that any changes to the protocol must be approved by the Sponsor or their representative prior to seeking approval from the IRB/EC. When the changes involved are only logistical and administrative in nature to trial this may not require prior approval by the IRB/EC. The Principal Investigator will be responsible for enrolling only those patients who have met protocol eligibility criteria.

CONFIDENTIAL Page **68** of **72**

12. PUBLICATION POLICY

12.1. Sponsor's Publication Policy

Sponsor or its designee shall have the right to publish or otherwise publicly disclose the information contained in or related to the Study Drug, the Study Data, or other Confidential Information in any form without the written consent of Site, the Principal Investigator or any other person. Each of Site and Principal Investigator further agrees that Sponsor shall have the exclusive right to commercialize any products or services that are based upon, or derived from the Study Drug, the Study Data, or other Confidential Information.

12.2. Site Publication

After the Study is completed, which means that all completed eCRFs have been received by Sponsor, and the database has been locked at all participating sites and Study closeout visits have taken place at all participating sites, then Site shall have the right, subject to the HIPAA Rules, to publish or otherwise make public data resulting from the conduct of the Study at the Site upon the earlier of (a) the date of publication of a multi-center publication coordinated by Sponsor with respect to the data resulting from the Study, and (b) the date of submission of the data resulting from the Study by Sponsor to the FDA for regulatory approval; provided that Site shall furnish Sponsor with a copy of any proposed publication or release at least 90 days in advance of the proposed submission or presentation date. Within this 90-day period, the Sponsor shall review such proposed publication or release to determine whether it contains any Confidential Information (other than Study Data), or whether Sponsor desires to file patent applications on subject matter contained therein, and to ensure the accuracy of the information contained in the publication or release. Upon receiving any notification from Sponsor requesting deletion of Confidential Information (other than Study Data), requesting correction of inaccuracies, or requesting a delay in publication of up to 90 days to allow the filing of patent applications before publication or release. Site shall take the requested action. The parties acknowledge and agree that Site shall be solely responsible for the editorial content of any such publication or release. In a manner consistent with customary practice. Site shall acknowledge the support and contributions of Sponsor, if requested by Sponsor, in connection with the Study, in any and all publications and presentations reporting and data resulting from the Study. Site and the Principal Investigator shall comply with all applicable federal and state laws and other applicable rules and requirements regarding disclosure of industry support (financial or otherwise) in connection with such publications and presentations.

CONFIDENTIAL Page **69** of **72**

## ABBREVIATIONS

Abbreviation	Definition
AE	Adverse Event
ACR	American College of Rheumatology
ANCOVA	Analysis of Covariance
APR	Accurate Pain Reporting
AUE	Area Under the Effect Curve
BMI	Body Mass Index
CI	Confidence Interval
cm	Centimeter
CRF	Case Report Form
CSR	Clinical Study Report
EOS	End of Study
EQ	EuroQol
EQ-5D-5L	EQ 5 Dimensions 5 Levels questionnaire
EQ VAS	EQ Visual Analogue Scale
EULAR	European League Against Rheumatism
FAS	Full Analysis Set
HIV	Human Immunodeficiency Virus
HOOS-QOL	Hip Injury and Osteoarthritis Outcome Score – Quality of Life Subscale
IA	Intra-articular
ICH	International Conference on Harmonization
JSN	Joint Space Narrowing
K-L	Kellgren-Lawrence
kg	Kilogram
LS	Least Squares
m	Meter
MedDRA	Medical Dictionary for Regulatory Activities
mg	Milligram
MMRM	Mixed Model for Repeated Measures
NRS	Numeric Rating Scale
OA	Osteoarthritis
OARSI	Osteoarthritis Research Society International
OLE	Open Label Extension
OMERACT	Outcome Measures in Rheumatology

Abbreviation	Definition
OR	Odds Ratio
PDF	Portable Document Format
PGIC	Patients' Global Impression of Change
PT	Preferred Term
SAE	Serious Adverse Event
SAP	Statistical Analysis Plan
SD	Standard Deviation
SI	Sleep Interference
SOC	System Organ Class
SP	Safety Population
TA 	Triamcinolone Acetonide
TEAE	Treatment Emergent AE
TSQM	Treatment Satisfaction Questionnaire for Medication
US	United States
WHO	World Health Organization
WOMAC	Western Ontario and McMaster Universities Osteoarthritis Index

 Abbreviated in past protocols and documents as TCA

## 1. INTRODUCTION AND OBJECTIVES OF ANALYSIS

### 1.1. Introduction

Osteoarthritis (OA) is a painful and debilitating musculoskeletal disease that is characterized by intra-articular (IA) inflammation, deterioration of articular cartilage, and degenerative changes to peri-articular and subchondral bone (Creamer and Hochberg, 1997; Goldring and Goldring, 2006). Arthritis is the most common cause of disability in the United States (US) and OA is the most common joints disease, affecting over 30 million Americans, with numbers expected to grow as a result of aging, obesity and sports injuries ([Woolf, 2003](#); [Cisternas, 2016](#); [Martel-Pelletier, 2008](#); [Michael, 2010](#)). Recent data suggest that OA accounts for over \$185 billion of annual healthcare expenditures in the US, which does not include loss of productivity costs. It is estimated that by 2030, 45 million people will have OA. OA commonly affects large weight-bearing joints like the knees and hips, but also occurs in the shoulders, hands, feet and spine. Patients with OA suffer from joint pain, tenderness, stiffness and limited movement. As the disease progresses, it becomes increasingly painful and debilitating, culminating, in many cases, in the need for total joint arthroplasty.

Current Guidelines from the American College of Rheumatology (ACR), Osteoarthritis Research Society International (OARSI) and the European League against Rheumatism (EULAR) recommend the use of IA corticosteroids for short-term acute pain relief (Hochberg et al, 2012; Jordan et al, 2003; Menge et al, 2014).

The prevalence of hip OA is estimated to range from 6.7% to 9.2% among adults  $\geq 45$  years of age and increases with age (Lawrence et al, 2008; Murphy et al, 2012). It is recognized that chronic inflammation occurs in all stages of OA (Benito et al, 2005; Sellam and Berenbaum, 2010; Wenham and Conaghan, 2010). As inflammation is correlated with clinical symptoms and joint degeneration, it should be an important target for corticosteroid intervention.

FX006 is an extended-release formulation of triamcinolone acetonide (TA) for IA administration. It is approved in the US under the trade name ZILRETTA® (triamcinolone acetonide extended-release injectable suspension) for the management of pain of OA of the knee. FX006 is intended to deliver TA to the synovial and peri-synovial tissues for a period of approximately 3 months (Bodick et al, 2013). FX006 contains TA, United States Pharmacopeia (Ph. Eur/USP), formulated in 75:25 poly (lactic-co-glycolic acid) (PLGA) microspheres with a nominal drug load of 25% (weight by weight [w/w]) and is provided as a sterile white to off-white powder for reconstitution. The drug product is reconstituted with diluent containing an isotonic, sterile aqueous solution of sodium chloride (NaCl; 0.9% w/w), carboxymethylcellulose sodium (CMC; 0.5% w/w) and polysorbate-80 (0.1% w/w) to form a suspension prior to IA injection.

Similar as in knee OA, hip OA patients are confronted with insufficient management of their symptoms (Zhang et al, 2008). Conventional corticosteroids have demonstrated clinical benefits in patients with hip OA (Lambert et al, 2007; Qvistgaard et al, 2006; Atchia et al, 2011), but with short duration of effect (approximately 4-8 weeks) and side effects from burst release of steroids into systemic circulation (Habib et al, 2011). Due to its slow release formulation,

---

FX006 has the potential to offer longer duration of efficacy and minimized systemic exposure, thus, an improved benefits/risk profile for hip OA patients.

